# 2 LAY SUMMARY

This is a trial of a new vaccine against Nipah virus. Nipah virus is a potentially fatal infection that can cause severe breathing problems and abnormalities with the nervous system including the brain. It was first identified in 1999 in a large outbreak in Malaysia and Singapore which was caused by

RECRef: 23/SC/0268 NIV001: A study of a new vaccine against Nipah Page 6 of 71

transmission from infected pigs to humans. Since then, outbreaks have occurred almost annually in Bangladesh with human-to-human spread. The virus has the potential to cause large outbreaks. There are no approved treatments or vaccines.

This study is of a vaccine called ChAdOx1 NipahB which has been developed by The University of Oxford. The vaccine is similar to the Oxford/AstraZeneca COVID-19 vaccine, however, the trial vaccine targets a component of the Nipah virus rather than the virus that causes COVID-19. This trial will be the first time the vaccine is given to humans. The purpose is to assess the safety and immune response.

We will recruit 51 healthy people aged 18 to 55 years. Participants will be screened for eligibility with an online questionnaire and telephone call, followed by an in-person medical assessment. The first 6 eligible participants will have two doses of vaccine 12 weeks apart. The following 45 participants will be assigned, at random, to one of three groups. Group 1 will receive one dose of vaccine and one dose of sterile salt water, group 2 will receive two doses of vaccine, and group 3 will receive two doses of sterile salt water. The intramuscular injections will be given 12 weeks apart. The sterile salt water has no active ingredients which means it acts as a 'placebo'. Apart from the researchers responsible for the randomisation, preparation and administration of the vaccine, the study team nor the participants will know whether vaccine or placebo were given until the end of the study. Participants will be followed up for 1 year from the first vaccination.

RECRef: 23/SC/0268 NIV001: A study of a new vaccine against Nipah Page 7 of 71 IRAS project ID: 1007433 Virus in adults aged 18 to 55

# 3 SYNOPSIS

Trial Title	A phase I safety and immunogenicity study of a Nipah virus vaccine, ChAdOx1 NipahB, in											
	healthy vo	lunteers aged 1	8 to 55 in the UK									
Trial Site(s)	Site 1 (Rec											
		Oxford Vaccine Group, Centre for Clinical Vaccinology and Tropical Medicine (CCVTM), [name]										
	-											
	Site 2 (Non-Recruiting): Oxford University Hospital Foundation Trust Laboratories (OUHFT)											
Funder	Coalition for Epidemic Preparedness Innovations (CEPI)											
Trial Code	NIV001											
Study Design	First-in-hui	man, phase I cli	nical trial with an initial ope	en-label non-randomised l	ead-in cohort							
-		=	oarticipant-observer blind c									
	ChAdOx1 N	lipahB, two-dos	se ChAdOx1 NipahB, or plac	ebo, respectively (cohort	2)							
Vaccine Schedule	1 dose give	en at week 0, or	2 doses given at 0 and 12 v	weeks								
Population	Healthy ac	lults aged 18 to	55 years with no adenov	riral-vectored vaccine exp	osure within the							
	preceding	year										
Planned Study Size	51 particip	ants (6 in cohor	t 1; 45 in cohort 2)									
Follow-up Duration	12 months											
Planned Trial Period	Q3 2023 to	Q4 2024										
Primary Objective	To assess t	he safety and to	olerability of ChAdOx1 Nipa	hB in healthy adult volunt	eers							
Secondary Objective	To assess t	he immunogen	icity of ChAdOx1 NipahB in	healthy adult volunteers								
Investigational	1. ChAdO	0x1 NipahB (5 ×	10  viral particles (vp) per	dose administration)								
Products	2. Placeb	o comparator:	0.9% sodium chloride (salin	e) injection								
Route	Intramuscı	ularly (IM) into t	the deltoid region of the arr	n								
Cohort	Group	Number of Participants	Intervention 1 (Week 0)	Intervention 2 (Week 12)	Follow-up Period							
1	А	6	5 × 10  vp ChAdOx1 NipahB	5 × 10  vp ChAdOx1 NipahB	1 year							
2	1	1 20 $5 \times 10^{10}$ vp ChAdOx1 Saline placebo 1 year										
	2	2 20 5 × 10  vp ChAdOx1 5 × 10  vp ChAdOx1 1 year NipahB										
	3	5	Saline placebo	Saline placebo	1 year							

RECRef: 23/SC/0268 NIV001: A study of a new vaccine against Nipah Page 8 of 71 Virus in adults aged 18 to 55

Virus in adults aged 18 to 55 Protocol V4.0, 16 AUG 2024

### 4 SCHEDULE OF PROCEDURES TABLE

# 4.1 Schedule of Procedures Table: Screening Visit (all volunteers)

Table 1 Schedule of Procedures: Screening Visit (all volunteers)

Visit Number	S
Visit type	Screening
Timeline 	0 to 90 days before D0
Visit Procedures	
Informed consent	Х
Review inclusion and exclusion criteria	X
Record demographic data	Х
Medical history 	Χ
Vital signs (heart rate, temperature,	Χ
blood pressure) and height and	
weight	
Screening physical examination	Χ
TOPS initial check	X
www.tops.org.uk	
Record emergency contact	X
information	
Urine Samples	
Highly Sensitive Urinary hCG (WOCBP	Х
only)	
Blood Samples 	
HBsAg, HCV Ab, HIV serology (mL)	~5
Biochemistry, haematology (mL)	~5
Blood volume per visit (mL)	~10
Cumulative blood volume (mL)	~10

<sup>1Additional unscheduled screening visits may occur (for example: to repeat a blood test)

TOPS: The Over-volunteering Prevention System; WOCBP: women of child bearing potential  $\,$ 

RECRef: 23/SC/0268 NIV001: A study of a new vaccine against Nipah Page 9 of 71 IRAS project ID: 1007433 Virus in adults aged 18 to 55

<sup>2Medical history may be initially assessed by a telephone call prior to screening (section 9.2)

<sup>3Minor differences in blood volumes may occur depending on the collection tubes and equipment used (~ = approximately); additional repeat blood draws may be required (for example: if there is a problem with the sample or abnormality in the results)

#### 4.2 Schedule of Procedures Table: Vaccination and Follow up Visits (Cohort 1)

 Table 2 Schedule of Procedures Table: Vaccination and Follow up Visits (Cohort 1)

Visit Number	1	2	3	4	5	6	7	8	9	10	11	12	13
Visit type	Vac1	f/u	f/u	f/u	f/u	f/u	Vac2	f/u	f/u	f/u	f/u	f/u	f/u
Timeline 	D0	D2	D7	D14	D28	D56	V2 (D84)	V2 +2	V2 +7	V2 +14	V2 +28	V2 +56	V2 +281
Time window (days)		±1	±2	±3	±3	±7	±14	±1	±2	±3	±3	±7	±60
Visit Procedures													
Review contraindications, inclusion and exclusion criteria	х						Х						
Vaccination (and immediate post-vaccination observation period)	х						Х						
Vital signs (heart rate, temperature, blood pressure)	х	х	х	х	х	х	Х	х	х	х	х	Х	
Targeted medical history/physical examination (if required)	(X)	(X)	(X)	(X)	(X)	(X)	(X)	(X)	(X)	(X)	(X)	(X)	(X)
Adverse Event													
Collection Solicited AE													
collection	D	0 to D6	5				V2 to	V2+6	days				
Unsolicited AE collection		D	) to D2	7				V2 to	V2+27	days			
SAEs & AESI collection	Х	Х	Х	Х	Х	Х	Х	Х	Х	Х	Х	Х	Х
Review ongoing AEs		Х	Х	Х	Х	Х	Х	Х	Х	Х	Х	Х	Х
Electronic diary (eDiary) 													
Electronic diary started	Х						Х						
Electronic diary review (in clinic)		Х	Х	Х	Х			Х	Х	Х	Х		
Electronic diary closed					Х						Х		
Urine Samples													
Highly Sensitive Urinary hCG (WOCBP only)	Х						Х						Х
Blood Samples 													
HLA typing (mL)	~4												

RECRef: 23/SC/0268 Page 10 of 71 NIV001: A study of a new vaccine against Nipah

Biochemistry, Haematology (mL) [LFTs, U+Es, FBC]	~5	~5	~5	~5	~5	~5	~5	~5	~5	~5	~5	~5	
Immunology (mL)	~60			~60	~50	~50	~50			~60	~70	~50	~50
Blood volume per visit (mL)	~69	~5	~5	~65	~55	~55	~55	~5	~5	~65	~75	~55	~50
Cumulative blood volume (mL)	~79	~84	~89	~154	~209	~264	~319	~324	~329	~394	~469	~524	~574

<sup>1Additional unscheduled visits may occur (for example: to repeat a blood test or for additional clinical review) eDiaries are remotely monitored in (near) real-time for the occurrence of grade ≥3 AEs and daily for non-completion

WOCBP: women of child bearing potential

RECRef: 23/SC/0268 NIV001: A study of a new vaccine against Nipah Page 11 of 71 IRAS project ID: 1007433 Virus in adults aged 18 to 55

 $^{3}$ Minor differences in blood volumes may occur depending on the collection tubes and equipment used ( $^{\sim}$  = approximately); additional repeat blood draws may be required (for example: if there is a problem with the sample, abnormality in the results, or participant unwell)

# 4.3 Schedule of Procedures Table: Vaccination and Follow up Visits (Cohort 2)

Table 3 Schedule of Procedures Table: Vaccination and Follow up Visits (Cohort 2)

Visit Number	1	2	3	4	5	6	7	8	9
Visit type	Vac1	f/u	f/u	f/u	Vac2	f/u	f/u	f/u	f/u
Timeline 	D0	D1	D14	D28	V2 (D84)	V2+1	V2+14	V2+28	V2+281
Time window (days)		+1	±3	±3	±14	+1	±3	±3	±60
Visit Procedures									
Review contraindications, inclusion and exclusion criteria	Х				х				
Randomisation	Х								
Vaccination (and immediate post-vaccination observation period)	Х				Х				
Vital signs (heart rate, temperature, blood pressure)	Х	Х	Х	х	Х	Х	Х	Х	
Targeted medical history/physical examination, if required	(X)	(X)	(X)	(X)	(X)	(X)	(X)	(X)	(X)
Adverse Event Collection									
Solicited AE collection	D0 t	o D6			V2 to V2	2+6 days			
Unsolicited AE collection		D0 to	D27			V2 to V2	+27 days		
SAEs & AESI collection	Х	Х	Х	Х	Х	Х	Х	Х	Х
Review ongoing AEs		Х	Х	Х	Х	Х	Х	Х	Х
Electronic diary (eDiary) 									
Electronic diary started	Х				Х				
Electronic diary review (in clinic)		Х	Х	Х		Х	Х	Х	
Electronic diary closed				Х				Х	
Urine Samples									
Highly Sensitive Urinary hCG (WOCBP only)	Х				Х				Х
Blood Samples 									
HLA typing (mL)	~4								
Biochemistry, Haematology (mL) [LFTs, U+Es, FBC]	~5	~5	~5	~5	~5	~5	~5	~5	
Immunology (mL)	~60		~60	~50	~50		~60	~70	~50
Blood volume per visit (mL)	~69	~5	~65	~55	~55	~5	~65	~75	~50
Cumulative blood volume (mL)	~79	~84	~149	~204	~259	~264	~329	~404	~454

<sup>1Additional unscheduled visits may occur (for example: to repeat a blood test or for additional clinical review)

RECRef: 23/SC/0268 NIV001: A study of a new vaccine against Nipah Page 12 of 71 IRAS project ID: 1007433 Virus in adults aged 18 to 55

Virus in adults aged 18 to 55 Protocol V4.0, 16 AUG 2024

<sup>2eDiaries are remotely monitored in (near) real-time for the occurrence of grade ≥3 AEs and daily for non-completion³Minor differences in blood volumes may occur depending on the collection tubes and equipment used (~ = approximately); additional repeat blood draws may be required (for example: if there is a problem with the sample, abnormality in the results, or participant unwell). WOCBP: women of child bearing potential

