### **6 OBJECTIVES AND ENDPOINTS**

# 6.1 Objectives, Outcome Measures and Evaluation Timepoints

Outcome	Objective	Outcome measure	Evaluation timepoints 
Primary	To assess the safety and tolerability of ChAdOx1 NipahB in healthy volunteers aged 18-55	a) Occurrence of solicited local reactogenicity signs and symptoms b) Occurrence of solicited systemic reactogenicity signs and symptoms c) Occurrence of unsolicited adverse events (AEs) d) Occurrence of abnormal safety laboratory measures	7 days following each vaccination
		e) Occurrence of serious adverse events (SAEs) and adverse events of special interest (AESIs)	Cohort 2 : D0, D1, D14, D28, V2, V2+1, V2+14, V2+28 Duration of the study (D0 to V2+281)
Secondary	To assess the immunogenicity of ChAdOx1 NipahB vaccine in healthy adult volunteers aged 18-55	NipahB glycoprotein G-specific serological response as measured by ELISA	Cohort 1: D0, D14, D28, D56, V2, V2+14, V2+28, V2+56, V2+281 Cohort 2: D0, D14, D28, V2, V2+14, V2+28, V2+281
Exploratory 	Immunological profiling	a) NipahB neutralising antibody responses measured by live or pseudoneutralisation assays b) NipahB glycoprotein G T cell response measured by IFN-g ELISPOT c) Cellular immune response to Nipah virus measured by ICS, proliferation and/or whole blood assays	Timepoints will be detailed in the laboratory analysis plan
	To assess anti-PF4 antibody levels following vaccination	Change in anti-PF4 antibody level measured by ELISA	D0, D14, V2+14
	To assess anti-vector immunity following vaccination	Binding and/or neutralising antibody responses against ChAdOx1	Timepoints will be detailed in the laboratory analysis plan

Visit and procedure timepoint windows are defined in section 4 (Schedule of Procedures). These exploratory endpoints may be performed; additionally, sample analysis for the completion of exploratory endpoints may be performed under the ethically-approved Oxford Vaccine Centre (OVC) Biobank protocol (REC 21/SC/0161). Further exploratory assays/analyses may be carried out (see section 9.6.2).

RECRef: 23/SC/0268 NIV001: A study of a new vaccine against Nipah Page 26 of 71

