# 11.8 Unsolicited Adverse Events

Unsolicited adverse events i.e. those collected through open questioning e.g. "did you experience any new symptoms?" (which are not solicited adverse events on days 0-6 following vaccination and do not constitute SAEs or AESIs) will be collected for 28 days (on days 0-27) following administration of the IMP. These will be recorded in the participant's eDiary and then recorded by the study team in the relevant eCRF.

RECRef: 23/SC/0268 NIV001: A study of a new vaccine against Nipah Page 45 of 71 IRAS project ID: 1007433 Virus in adults aged 18 to 55

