#### 11.9.2 eDiary Collection of Unsolicited Adverse Events

From the time of each vaccine administration up to 28 days post-vaccination (day of vaccination and 27 subsequent days), unsolicited adverse events will be collected using the eDiary and reviewed at clinic visits. If a participant records a grade 3 or 4 adverse event, an email alert is sent to the investigator(s), so that the investigator is aware and can review appropriately. If clarification of any event is required then the study nurse or doctor will seek this from the participant during a clinic visit or by telephone call. These unsolicited adverse events will be recorded in the AE section of the eCRF. Unsolicited adverse events recorded in the eDiary will be severity-graded by the participant. Causality will be assigned by the blinded PI-delegated clinician / Investigator as per section 11.3.

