## 11.22.1 DSMC Reviews

DSMC data reviews will be done as follows:

- 1. Formal review of the safety profile data after 7 days following the first vaccination of all 6 participants in Cohort 1. This review will decide on progression to administering the first dose of vaccine to the remaining participants (Cohort 2) in the trial.
- 2. Formal review of the immunological and safety profile including data up to 28 days after the first dose of vaccine has been administered to all participants in Cohort 1 and the first 18

RECRef: 23/SC/0268 NIV001: A study of a new vaccine against Nipah Page 49 of 71 IRAS project ID: 1007433 Virus in adults aged 18 to 55

participants in Cohort 2 (total 24 participants). The trial will continue in parallel to this DSMC review.

- 3. Formal review of the immunological and safety profile including data up to 28 days after the first dose of vaccine has been administered to all participants. The trial will continue in parallel to this DSMC review.
- 4. Formal review of the safety profile data after 7 days following the second vaccination of participants in Cohort 1. This review will decide on progression to administering the second dose of vaccine to the participants in Cohort 2.
- 5. Formal review of the immunological and safety profile including data up to 28 days after the second dose of vaccine has been administered to all participants.
- 6. Independent review following any SAE deemed to be related to the trial active vaccine or placebo.
- 7. Unscheduled reviews on request of the study management committee at a frequency determined by the severity of reported adverse events.

From these reviews the DSMC will make recommendations to the study investigators on whether there are any ethical or safety reasons why the trial should not continue. A summary of all blinded and unblinded AEs and SAEs to date will be provided to the DSMC on request.

The outcome of each DSMC review will be communicated directly to the TMG and documentation of all reviews will be kept in the TMF.

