#### 13 STATISTICS

#### 13.1 Study Analyses

# 13.1.1 Descriptive Statistical Methods

The analyses for this study will be descriptive in purpose and will not include any hypothesis testing, power calculations, or presentation of p-values for group comparisons.

Counts and percentages of local and systemic solicited adverse reactions from eDiaries during days 0-6 following each vaccination will be presented for each group. Unsolicited AEs occurring during days 0-27 following each vaccination, and all SAEs and AESIs occurring throughout the duration of the study will be summarised.

Highly skewed antibody and cellular response data will be log-transformed prior to analysis. The geometric mean titres (GMTs) and associated 95% confidence intervals (CIs) will be summarised by computing the anti-log of the mean of the log-transformed data. Medians and interquartile ranges of the untransformed data may additionally be presented.

Due to the descriptive nature of the trial, no testing will be performed between groups.

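### The eDiary is scheduled to close at visits that may validly fall on days 25 to 27, so prospective capture of unsolicited AEs can stop before the days 0-27 window ends

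*Protocol*

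**What the plan says.** The occurrence of unsolicited AEs is primary outcome (c) in Protocol section 6.1. Four places bear on how long it is observed.

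- **Definition.** Section 11.8 says these events "will be collected for 28 days (on days 0-27) following administration of the IMP", entered first in the participant's eDiary and then by staff in the eCRF.
- **Tool.** Section 11.9.2 has the diary in use for the whole period: "up to 28 days post-vaccination (day of vaccination and 27 subsequent days), unsolicited adverse events will be collected using the eDiary".
- **Analysis.** Section 13.1.1 summarises "Unsolicited AEs occurring during days 0-27 following each vaccination".
- **Schedule.** Tables 2 and 3 (sections 4.2 and 4.3) carry an unsolicited-AE row running from D0 to D27 and from V2 to V2+27. The row "Electronic diary closed" is marked at D28 and V2+28: visits 5 and 11 in Cohort 1, visits 4 and 8 in Cohort 2. All four visits have a window of ±3 days, and section 9.4 expects visits to take place within their windows.

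Footnote 2 to both tables says the diary is monitored remotely for events of grade 3 or higher and daily for non-completion. Section 11.9.2 adds an email alert for grade 3 or 4 entries. The DSMC reviews in section 11.22.1 use data to 28 days after dosing; the third, for example, is described as "including data up to 28 days after the first dose of vaccine has been administered to all participants".

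**The concern.** The end of diary collection is fixed in two ways that agree only when the visit falls on day 28 or later. The text fixes it by days since vaccination; the schedule fixes it by a visit that may come up to three days early. No sentence in the protocol keeps the diary open after an early visit.

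If staff follow the table, participants seen early stop making prospective entries, and the automatic grade 3 or higher alert stops with them, while the unsolicited-AE window is still running. Section 11.6 makes the gap matter more. Outside the 28-day period, non-serious AEs are recorded only if they needed medical attention. For a mild event on day 26 that is first mentioned at a much later visit, staff would have to rely on a recalled onset date to decide whether it counts. At stake is complete ascertainment of a primary safety outcome in a first-in-human trial, and any shortfall runs in one direction only.

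**Working it through.** **Inputs.** Collection window: days 0 to 27 (sections 11.8, 11.9.2, 13.1.1). Closing visit: nominal day 28 ± 3 (Tables 2 and 3). Next scheduled visits and their windows: Tables 2 and 3. Participants: 51, of whom 45 are in Cohort 2 (section 7.1).

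**The plan's own figure.** Window length = 27 − 0 + 1 = 28 days, as stated.

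**Earliest valid closure.** 28 − 3 = day 25; the latest is 28 + 3 = day 31.

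**Diary days lost when the diary closes at a visit on day v.** Whole days lost = max(0, 27 − v). The upper bound also counts the visit day, as if nothing were captured on it: max(0, 28 − v).

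| Visit day | Whole days lost | Share of 28 | Upper bound incl. visit day | Share of 28 |
|---|---|---|---|---|
| 25 | 2 (days 26, 27) | 7.1% | 3 | 10.7% |
| 26 | 1 (day 27) | 3.6% | 2 | 7.1% |
| 27 | 0 | 0% | 1 | 3.6% |
| 28 to 31 | 0 | 0% | 0 | 0% |

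The whole-day column is nearer the truth, because both tables schedule an in-clinic diary review at the closing visit. Part of the visit day is therefore captured.

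**Illustration.** The documents do not say how visit dates will be distributed. If they were spread evenly over days 25 to 31 (an assumption):

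- 3/7 = 43% of visits would fall before day 28, and 2/7 = 29% would lose at least one whole day.
- Mean whole days lost = (2 + 1 + 0)/7 = 0.43, or 0.43/28 = 1.5%.
- Mean upper bound = (3 + 2 + 1)/7 = 0.86, or 0.86/28 = 3.1%.

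There are at most 51 × 2 = 102 dose windows. Only those with an early closing visit are affected.

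**How long until staff next ask.** The interval runs from an event on day 26 or 27 to the next scheduled visit, allowing for that visit's window.

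- Cohort 1, D56 ± 7 or V2+56 ± 7: from 49 − 27 = 22 to 63 − 26 = 37 days.
- Cohort 2 after dose 1, V2 at D84 ± 14: from 70 − 27 = 43 to 98 − 26 = 72 days, about 6 to 10 weeks.
- Cohort 2 after dose 2, V2+281 ± 60: from 221 − 27 = 194 to 341 − 26 = 315 days, about 6 to 10 months.

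Cohort 2 holds 45 of the 51 participants, so the long intervals are the usual case.

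**The case against.** The strongest reply is that the collection window itself is never cut. Every definition of it counts days since vaccination, the tables show the D0 to D27 row separately from the visit columns, and the closure mark can be read as a checklist entry at nominal day 28, which fits days 0-27. Section 12 leaves data-management detail to a separate plan, so the system may already stay open to day 27. Other routes also exist. Section 11.6 allows recording in the eDiary, the eCRF or both, and sections 9.4.1, 9.4.2 and 11.11 have AEs elicited at later visits. SAEs and AESIs are collected throughout, and medically attended AEs are recorded even after 28 days.

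Much of this stands, and it rules out several stronger readings that a reader might infer:

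- **That the observation window varies from 25 to 28 days between participants.** The documents do not support this. The window is fixed; only prospective diary capture can end early.
- **That the diary is the only means of capture.** It is the only participant-entered daily record, but recall at visits and eCRF entry remain.
- **That the reported event rate is understated.** This would need early visits, events in the exposed days, and failure to pick them up later. Lost diary days are not the same as lost events.
- **That the DSMC would receive 25-day data labelled as 28-day data.** The review descriptions set how far the data extend; they do not promise 28 complete diary days.

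What the reply does not remove is the mismatch on the page. A member of staff who follows Table 2 or 3 at a day-25 visit would close a diary that section 11.9.2 requires to run for two more whole days. In Cohort 2 the recall backup is weak.

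**Conclusion.** The point holds as an inconsistency between the schedule tables and sections 11.8, 11.9.2 and 13.1.1, with a limited consequence. Followed as scheduled, an early closing visit ends prospective eDiary capture and its alerts by up to two whole days (7.1% of the window) plus the rest of the visit day (upper bound 10.7%), after either dose and in both cohorts.

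The exposure is mainly to minor, non-serious AEs without medical attention in the tail of the window. The effect is likely small. Nothing in the documents links early visits to arm in the blinded cohort, and the trial makes no between-group tests, so bias between groups is not the issue. The size depends on how many visits fall on days 25 to 27, which the documents do not give, and on the diary actually being closed at the visit as the tables indicate. The change is worth making because it costs almost nothing and protects a primary safety outcome.

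**What to change.** Reconcile Tables 2 and 3 with section 11.9.2 by stating that the eDiary closes after the day-27 entry (V2+27 for the second dose), whatever the date of the D28 or V2+28 visit. For participants seen before day 28, add a brief remote check of the remaining entries on or after day 28. If the system is already set up this way, the tables need only say so.

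Keep the ±3-day visit window. Making it forward-only would also solve the problem, but it would narrow the window from seven days (25 to 31) to four (28 to 31) for visits that also supply safety bloods and ELISA samples.

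The cost is one changed line in each table, one eDiary setting, and a short contact for those seen early. No additional samples or participants are needed.
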